7.6.4. Management of Elevated Serum Creatinine and Decreased Creatinine Clearance

- Glomerular filtration rate (estimated creatinine clearance) will be calculated at each visit using the Schwartz Formula for subjects ages 2 to <12 as follows:

$$\text{Schwartz Formula (mL/min/1.73 m}^2\text{)} = k \times L/\text{Scr}$$

[(k is proportionality constant: pediatric males/females \geq 2 years to < 12 years $k = 0.55$; for adolescent females \geq 12 years old, $k = 0.55$, and for adolescent males \geq 12 years, $k = 0.70$); L is height in centimeters (cm); and Scr is serum creatinine (mg/dL)]

- If creatinine clearance decreases to < 50 mL/min/1.73 m² (confirmed) at any time during the study, study drug should be permanently discontinued, followed by 24 weeks of monthly monitoring in treatment-free follow up if alternative HBV therapy is not initiated.
- Subjects with estimated creatinine clearance < 70 mL/min/1.73 m² and serum creatinine increased ≥ 0.5 mg/dL above baseline should have the serum creatinine and creatinine clearance confirmed by repeating testing within three calendar days of receipt of results and before study drug discontinuation, unless such a delay is not consistent with good medical practice.

- Subjects with confirmed estimated creatinine clearance $< 70 \text{ mL/min/1.73 m}^2$ and serum creatinine increased $\geq 0.5 \text{ mg/dL}$ above baseline should have study medication discontinued, and the subject should be followed weekly for two weeks. After two weeks, if the estimated creatinine clearance is $\geq 70 \text{ mL/min/1.73 m}^2$, study medication may be resumed, with monitoring as described below. If the estimated estimated creatinine clearance remains $< 70 \text{ mL/min/1.73 m}^2$, study drug should be permanently discontinued, followed by 24 weeks of monthly monitoring in treatment-free follow up if alternative HBV therapy is not initiated.
- The serum creatinine and estimated creatinine clearance should be rechecked within two weeks after restarting treatment to ensure that the subject has stabilized. Once this has been determined, the subject should be evaluated at regularly scheduled study visits.
- If creatinine clearance decreases to $< 70 \text{ mL/min/1.73 m}^2$ (confirmed) following rechallenge with study drug, study drug should be permanently discontinued, followed by 24 weeks of monthly monitoring in treatment-free follow up if alternative HBV therapy is not initiated.

7.6.5. Special Considerations During Blinded Treatment – Grade 4 ALT Management

Subjects who experience Grade 4 ALT while on blinded study medication will be evaluated weekly with serum chemistry and liver function test monitoring. In the event that any subject has sustained Grade 4 ALT for ≥ 16 weeks (i.e., failure to resolve ALT to grade ≤ 3 or baseline), the serial HBV DNA values on study will be provided to the investigator, and the subject can be offered open-label tenofovir DF, after discussion with the Gilead Medical Monitor.

7.6.6. On-Treatment ALT Flare and Post-Treatment Exacerbation of Hepatitis Management

For subjects with bridging fibrosis or cirrhosis, study drug discontinuation with treatment-free follow-up is contraindicated due to the potential risk of exacerbation of hepatitis in the setting of low hepatic reserve which could lead to decompensation. Subjects with bridging fibrosis or cirrhosis should be placed on commercially available HBV therapy following study drug discontinuation.

On-Treatment ALT Flare and Post-Treatment Exacerbation of Hepatitis are defined as:

- Serum ALT $> 2 \times$ baseline and $> 10 \times$ ULN, with or without associated symptoms OR
- Confirmed ALT elevation (defined as 1-grade shift or $2 \times$ previous value) associated with confirmed changes outside of the normal range in other laboratory parameters suggestive of worsening hepatic function (abnormal PT ≥ 2 seconds or INR ≥ 0.5 over baseline, abnormal serum albumin $\geq 1 \text{ g/dL}$ below baseline or elevated serum lactate levels (if available), defined as $2 \times$ ULN per the Adult AIDS Clinical Trials Group (AACTG) guidelines).

7.6.6.1. Management of ALT Flare in Subjects Receiving Study Medication

If laboratory results indicate (1) elevation of ALT $> 2 \times$ baseline and $> 10 \times$ ULN OR (2) abnormal laboratory parameters suggestive of worsening hepatic function (abnormal PT ≥ 2 sec above baseline, INR ≥ 0.5 above baseline, abnormal albumin ≥ 1 g/dL decrease from baseline or elevated serum lactate levels $> 2 \times$ ULN along with any ALT elevation (i.e., grade shift or $2 \times$ previous value), the following is recommended:

- Schedule the subject to return to the clinic as soon as possible and ideally no later than one week after the initial labs were drawn. During the visit, perform a clinical assessment of the subject. The assessment should include a physical examination and evaluation of the subject's mental status.
- Draw blood samples, request lactate testing and send for confirmation of elevated serum transaminases (ALT/AST), total bilirubin and PT/INR, and albumin. [Note: If, in the investigator's judgment, the central laboratory cannot provide adequate turn around time, the confirmation test may also be performed at a local laboratory. However, the central laboratory results are considered definitive].

If the elevations are confirmed, request the central clinical laboratory to conduct reflex testing for serum HBV DNA, HBV serology (HBeAg, HBeAb, and HBsAg), HDV, HAV IgM, and HCV serology.

Based on the results of the confirmatory tests, the following treatment modifications are recommended:

Elevated Liver Enzymes, Normal Bilirubin, Normal PT/INR, Normal Albumin, Normal Lactate

If ALT and/or AST levels are elevated (i.e., $> 2 \times$ baseline and $> 10 \times$ ULN) but total bilirubin and PT/INR, albumin and lactate are normal, the subject may remain on study medication and should be monitored every week until ALT/AST return to normal or baseline levels. During monitoring:

- If ALT/AST levels decline within 4 weeks, the subject should remain on study and return to the clinic per protocol.
- If after 4 weeks of monitoring, ALT/AST values remain elevated (e.g., $> 2 \times$ baseline and $> 10 \times$ ULN) or have worsened, with bilirubin $\leq 2.5 \times$ ULN, PT $\leq 1.5 \times$ ULN, or abnormal albumin or lactate levels, the investigator should consult with the Gilead Medical Monitor.

- If ALT remains $> 2 \times$ baseline and $> 10 \times$ ULN and the bilirubin or PT values are confirmed at $> 2.5 \times$ ULN or $> 1.5 \times$ ULN, respectively, the investigator should consider discontinuing study medication and initiating alternative HBV therapy (see below). However, prior to initiating alternative therapy, medical management of the subject should be discussed with the Gilead Medical Monitor. (Note: Once a subject has started alternative therapy, s/he must be discontinued from the study.)

Elevated Liver Enzymes, Elevated Bilirubin and PT/INR ($>$ Grade 2), Symptomatic Elevated Lactate ($> 2 \times$ ULN) or Asymptomatic Elevated Lactate ($> 4 \times$ ULN)

If ALT/AST values are elevated (i.e., $> 2 \times$ baseline and $> 10 \times$ ULN) and bilirubin or PT values are confirmed at $> 2.5 \times$ ULN or $> 1.5 \times$ ULN, respectively, or lactate levels are increased (symptomatic and $> 2 \times$ ULN or asymptomatic and $> 4 \times$ ULN) the investigator should consider discontinuing study medication and initiating alternative HBV treatment. The subject must be monitored weekly for as long as enzyme levels and bilirubin and PT/INR remain elevated or above baseline values. Refer to [Appendix 6](#) for specific guidelines for the management of symptomatic and asymptomatic hyperlactatemia.

- If the ALT/AST levels return to the baseline level and/or Grade 2 or lower during the first 8 weeks of monitoring, study medication may be resumed.
- If the ALT/AST levels, bilirubin, PT/INR or lactate levels remain elevated up through Week 8 or deteriorate at any point, the investigator should consult with the Gilead Medical Monitor.

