Appendix 5. Management of Clinical and Laboratory Adverse Events

Appendix 6. Lactic Acidosis Guidelines

Lactic acidosis and severe hepatomegaly with steatosis, including fatal cases, have been reported with the use of nucleoside analogues alone or in combination with other antiretrovirals. A majority of these cases have been in women. Obesity and prolonged nucleoside exposure may be risk factors; however, cases have also been reported in subjects with no known risk factors.

Guidelines for management of symptomatic hyperlactatemia and asymptomatic hyperlactatemia are outlined in Section A and B below and are derived from the AIDS Clinical Trials Group (ACTG) Lactic Acidosis Guidelines. Section C outlines venous lactate collection techniques.

Section A. Symptomatic Hyperlactatemia

Symptomatic hyperlactatemia is defined as a clinical suspicion of hyperlactatemia characterized by new, otherwise unexplained and persistent (≥ 2 weeks) occurrence of 1 or more of the following symptoms:

- Nausea and vomiting
- Abdominal pain or gastric discomfort
- Abdominal distention
- Increased LFTs
- Unexplained fatigue
- Dyspnea

AND

Venous lactate level greater than twice the upper normal limit (ULN) confirmed by repeat venous lactate analysis within 1 week and, if persistently elevated, arterial lactate with blood gas analysis.

If the repeat venous lactate is elevated confirmation with an arterial lactate specimen and arterial blood gas (pH, PO₂, PCO₂, bicarbonate, oxygen saturation) should be performed within 48 hours. If the arterial specimen contains lactate at a level more than two times the upper limit of normal, the patient should be discontinued from the study and alternative therapy instituted. Subjects should be monitored weekly until signs and symptoms resolve. Hyperlactatemia should be followed until levels return to below two times the ULN.

An elevated anion gap in a patient with metabolic acidosis suggests the diagnosis of lactic acidosis. It can be suspected when the sum of cations minus the sum of anions $[(Na^+ + K^+) - (Cl^- + HCO_3^-)]$ exceeds 18 mEq/L (18 mmol/L) in the absence of other causes of increased anion gap such as renal failure, salicylate ingestion or other poisoning, or significant ketonemia (e.g., diabetic ketoacidosis, alcohol).

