Management of symptomatic subjects with lactate levels of 1 to 2 times the ULN is left to the discretion of the Investigator. As some of the symptoms are sufficiently vague (e.g., fatigue) to be present in everyone, serial repeat testing is encouraged with plans to modify the regimen if the lactate level rises to greater than two times the ULN as outlined above.

Section B. Asymptomatic Hyperlactatemia

In ASYMPTOMATIC subjects, lactic acidosis will be defined as hyperlactatemia greater than four times the ULN. Any patient with a lactate level more than two times the ULN but less than or equal to four times the ULN, should be questioned closely for symptoms (described above) and have a repeat venous sample obtained in 1 week, and, if confirmed, subsequently at monthly intervals.

If the patient fulfills the definition for ASYMPTOMATIC hyperlactatemia, repeat venous lactate should be obtained within a week with confirmation of a more than 4-fold venous elevation in lactate by arterial lactate measurement and arterial blood gas (pH, PO₂, PCO₂, bicarbonate, oxygen saturation) within 48 hours. If confirmed, the patient should be discontinued from the study and alternative therapy instituted. Hyperlactatemia should be followed until levels return to below two times the ULN.

Section C. Specimen Collection

Venous lactate levels are highly dependent on collection techniques. It is therefore recommended that the instructions below be followed closely. High lactate levels should be repeated for verification. If carefully collected, venous lactate level is equivalent to an arterial collection in most clinical situations. If it is not possible to collect the specimen without hand clenching or prolonged tourniquet time, an arterial lactate should be considered, as this will help exclude falsely elevated lactate levels.

1. Have subject sit, relaxed for 5 minutes prior to venipuncture.
2. Instruct subject to not clench the fist before or during the procedure and to relax the hand as much as possible.
3. If possible, do not use a tourniquet. If a tourniquet is necessary, then apply tourniquet lightly and draw lactate first before the other samples with the tourniquet still in place.
4. Collect the blood in a chilled gray-top (sodium fluoride-potassium oxalate) tube.
5. Place the specimen immediately on ice and send to the laboratory for immediate processing, preferably within 30 minutes of collection.

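### In the severe branch of Section 7.6.6.1 the restart rule tests ALT/AST only, which does not agree with Sections 7.6, 7.6.2 and 7.6.3 or, for confirmed hyperlactatemia, with Appendix 6

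*Protocol*

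**What the plan says.** **Entry to the branch.** The second branch of Protocol Section 7.6.6.1 applies when ALT/AST exceeds both 2 × baseline and 10 × ULN and at least one of these is present: confirmed bilirubin above 2.5 × ULN, confirmed PT above 1.5 × ULN, or raised lactate (above 2 × ULN with symptoms, above 4 × ULN without).

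**Action.** At that point "the investigator should consider discontinuing study medication and initiating alternative HBV treatment". Weekly monitoring must go on "for as long as enzyme levels and bilirubin and PT/INR remain elevated or above baseline values". The paragraph then points to Appendix 6 "for specific guidelines for the management of symptomatic and asymptomatic hyperlactatemia".

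**The two bullets that follow.** If ALT/AST levels "return to the baseline level and/or Grade 2 or lower during the first 8 weeks of monitoring, study medication may be resumed". If ALT/AST, bilirubin, PT/INR or lactate "remain elevated up through Week 8 or deteriorate at any point, the investigator should consult with the Gilead Medical Monitor".

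**Appendix 6.** In Section A (symptomatic), once an arterial sample is above 2 × ULN, "the patient should be discontinued from the study and alternative therapy instituted". In Section B (asymptomatic, above 4 × ULN), the instruction is: "If confirmed, the patient should be discontinued from the study and alternative therapy instituted". Neither section provides for a restart.

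**General toxicity rules.** Section 7.6 treats a restart as something that comes after the adverse event has resolved, and asks for a discussion with the Medical Monitor first. Under Section 7.6.2, a confirmed, clinically significant Grade 3 laboratory abnormality judged related to drug means withholding drug until that same toxicity is Grade 2 or lower. Under Section 7.6.3, a confirmed, clinically significant Grade 4 laboratory abnormality judged related means permanent discontinuation.

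**The concern.** Bilirubin, PT or lactate is what separates this branch from the milder one before it, yet none of them appears in the restart condition. The bullet that does name them leads only to a consultation, and only if values persist through Week 8 or worsen. A child whose transaminases fall early while the other signal stays flat meets the first bullet and not the second.

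What is at stake is patient safety and uniform conduct. Two sites with the same child and the same results could act differently depending on which page they follow. Appendix 6 itself notes that fatal cases of lactic acidosis have been reported with nucleoside analogues. The rule applies to any subject receiving study medication, so it reaches beyond the 48-week blinded period.

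**Working it through.** No sample-size, power or error-rate figure is involved, so there is nothing to recompute. The check sets the rules side by side and follows two cases through them.

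**Grade bands (Appendix 4).** ALT: Grade 2 is > 2.5 to 5 × ULN; Grade 4 is > 10 × ULN. Bilirubin: Grade 3 is > 2.5 to 5 × ULN. PT: Grade 3 is > 1.5 to 3 × ULN. The bilirubin and PT triggers are therefore each the floor of Grade 3, and the ALT entry value is Grade 4.

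**Case 1: bilirubin.** Suppose ALT is 12 × ULN with baseline below 6 × ULN (12 / 2 = 6, so the 2 × baseline test is met) and confirmed bilirubin is 3 × ULN. Study drug is stopped and no alternative therapy is begun. At monitoring Week 4, ALT is 4 × ULN (Grade 2), AST likewise, and bilirubin is still 3 × ULN (Grade 3).

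| Rule | What it tests | Outcome at Week 4 |
|---|---|---|
| 7.6.6.1, restart bullet | ALT/AST at baseline or Grade 2 or lower within 8 weeks | Met: drug may be resumed |
| 7.6.6.1, consultation bullet | Any parameter still raised through Week 8, or worse | Not met: Week 8 not reached, nothing has worsened |
| 7.6, general rule | Event resolved, Medical Monitor consulted | Bilirubin has not resolved; the section does not say which abnormality must |
| 7.6.2, if judged related | That toxicity at Grade 2 or lower | Bilirubin is Grade 3: drug is withheld |
| 7.6.3, if related, confirmed and clinically significant | Grade 4 abnormality | ALT of 12 × ULN: permanent discontinuation |

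PT above 1.5 × ULN in place of bilirubin gives the same table. If the event is judged unrelated to drug, the last two rows fall away and only the general rule of Section 7.6 stands beside the restart bullet.

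**Case 2: lactate.** The cut-offs in Section 7.6.6.1 and Appendix 6 are the same: above 2 × ULN with symptoms, above 4 × ULN without. Appendix 6 first requires a repeat venous sample and arterial confirmation. Once that is obtained, it takes the patient out of the study. For the same patient, Section 7.6.6.1 says to consider stopping, and its restart bullet has no exception for lactate. The two cannot both be followed. The overlap is realistic, because Appendix 6 counts raised liver tests among its qualifying symptoms if they are new, unexplained and persistent, and every child in this branch has raised enzymes.

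The weekly-monitoring sentence names enzymes, bilirubin and PT/INR but not lactate. Lactate is followed only through Appendix 6.

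**The case against.** The strongest reply is that Section 7.6.6.1 should not be read alone. Section 7.6 already places a Medical Monitor discussion before a restart and presumes resolution. Sections 7.6.2 and 7.6.3 already cover drug-related Grade 3 and Grade 4 abnormalities. The restart is permissive, and the modifications in this section are introduced as recommendations. For lactate, the paragraph sends the site to Appendix 6, so the natural reading is that the appendix governs. The word "consider" can sensibly cover the time before arterial confirmation.

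Much of this stands. A reader might infer that nothing in the protocol stands between the site and a restart. The documents do not support that, because the Section 7.6 discussion applies. But that discussion is a procedural step: it sets no condition on bilirubin, PT or lactate. Sections 7.6.2 and 7.6.3 apply only where the abnormality is judged drug-related, and where they apply they disagree with the restart bullet rather than complete it. The pointer to Appendix 6 states no order of precedence.

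A reader might also see a contradiction between starting alternative HBV treatment and later resuming study drug. That does not hold. The Note in the same section settles it: "Once a subject has started alternative therapy, s/he must be discontinued from the study". Resumption can therefore concern only children who have not started alternative therapy.

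**Conclusion.** The inconsistency is real and should be corrected. In the severe branch, the restart condition leaves out the parameters that define the branch and does not agree with Sections 7.6, 7.6.2 and 7.6.3. For hyperlactatemia confirmed under Appendix 6, the section and the appendix give incompatible instructions.

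Few children are expected to be affected; that is an assumption, since the documents give no expected frequency. The lactate conflict does not extend to a first, unconfirmed value. The disagreement with Sections 7.6.2 and 7.6.3 is limited to abnormalities judged drug-related.

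A reader might infer that Week 48 responder counts would shift through the missing = failure rule. The documents give nothing from which to size such an effect, and the point does not bear on the sample size, the significance level or the primary analysis.

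One limit remains. Only the title of Appendix 5 (management of clinical and laboratory adverse events) is readable in the text available, so nothing here relies on its content.

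**What to change.** The sponsor's medical team should reconcile Protocol Sections 7.6, 7.6.2, 7.6.3 and 7.6.6.1 with Appendix 6, Sections A and B. One consistent restart rule for the severe branch, and one consistent action for confirmed hyperlactatemia, should appear wherever the subject is covered. Alternatively, the protocol should state which passage governs when they differ. Appendix 5 should be checked at the same time. Which clinical values and actions apply is for the medical team; none is proposed here.

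The cost is an amendment to wording in one part of the protocol and one appendix, with the usual ethics submission, and a letter to sites. If the reconciled text relies on serial lactate, the team should note that the weekly-monitoring sentence does not currently name it.

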7.6.6.2. Management of Exacerbation of Hepatitis in Subjects Who Have Discontinued Study Medication

If laboratory results indicate (1) an ALT elevation $> 2 \times$ baseline and $> 10 \times$ ULN OR (2) abnormal laboratory parameters suggestive of worsening hepatic function (abnormal PT ≥ 2 secs above baseline, abnormal albumin ≥ 1 g/dL below baseline or elevated lactate levels $> 2 \times$ ULN) along with any ALT elevation (i.e., 1 grade shift or $2 \times$ previous value) and the subject is on no post-study therapy for HBV, the following is recommended:

- Schedule the subject to return to the clinic as soon as possible and ideally no later than 1 week after the initial labs were drawn. During the visit, perform a clinical assessment of the subject. The assessment should include a physical examination and evaluation of the subject's mental status.
- Draw blood samples and request lactate testing and confirmation of elevated serum transaminases (ALT/AST), bilirubin, PT/INR, and albumin. [Note: If, in the investigator's judgment, the central lab cannot provide adequate turn around time, the confirmation test may also be performed at a local lab. However, the central lab results are considered definitive].

- If the elevations are confirmed (e.g., ALT > 2 × baseline and > 10 × ULN) OR (2) abnormal laboratory parameters suggestive of worsening hepatic function (abnormal PT ≥ 2 secs above baseline, abnormal albumin ≥ 1 g/dL below baseline, or elevated lactate levels > 2 × ULN) along with any ALT elevation (i.e., 1 grade shift or 2 × previous value), request the clinical laboratory to conduct reflex testing for serum HBV DNA, HBV serology (HBeAg, HBeAb, and HBsAg), HDV, HAV IgM and HCV. If serum HBV DNA is increasing, the investigator should consider immediate initiation of approved therapy.
- The subject should be followed until the abnormal ALT/AST values, PT/INR, albumin or lactate laboratory parameters return to normal or baseline up to a maximum of 6 months after the initial occurrence of the event. Refer to [Appendix 6](#) for specific guidelines for the management of symptomatic and asymptomatic hyperlactatemia.

7.7. Risks for Women of Childbearing Potential or During Pregnancy

The risks of treatment with tenofovir DF during pregnancy have not been evaluated in pregnant women. Animal studies do not indicate direct or indirect harmful effects of TDF with respect to pregnancy. Please refer to the latest version of the Investigator's Brochure for additional information.

